Study Assessments	Day - 30 to -1	Day -1	28±	56 +/- 7 days	100 +/- 14 days	112±7	180+/- 14 days	196± 14	280±14	12 month post HCT (+/- 30 days)	
Informed consent	×										
Tildrakizumab administration – 100 mg subcutaneously		×	×			×		×	×		
History, physical exam, weight, height*	×		×	×	×	×	×	×	×	×	
ECOG Performance Status and HCT-CI*	×										
HLA typing (donor and recipient)*	X										
CBC with differential ¹ , Comprehensive metabolic panel ^{2*}	×		×	×	×	×	×	×	×	×	
Infectious disease markers3*	×										
LVEF4*	×										
DLCO and FEV14*	×						×			×	
Disease evaluation ⁵ *	×				×					×	
Pregnancy test ⁶ *	×										
GVHD assessments ^{7*}			×	×	×	×	×	×	×	×	
AE assessments ⁸	×		×	×	×	×	×	×	×	×	
Chimerism ^{9*}			×								
CMV NAAT peripheral blood*			×	×	×	×					
EBV PCR peripheral blood			×	×	×	×					
Immune reconstitution*			×		×		×			×	

13 MCW Protocol No: PRO00035737

Version Date: 10/31/2022

STUDY	STUDY CALENDAR	NDAR										
		Baseline	Pre- Transplant				(Post-Tr	(Post-Transplant) (in Days)			Follow-Up	
Study Assessments	y,	Day – 30 to -1	Day -1	28± 3	56 +/- 7 days	100 +/- 14 days	112±7	180+/- 14 days	196± 14	280±14	12 month post HCT (+/- 30 days)	
Pharmacokinetic Labs and ADA testing						See	• footnote	10 for de	See footnote 10 for details and timepoints	mepoints		
Research (stool) sample collection			×					See fo	ootnote 11	See footnote 11 for details and timepoints	nd timepoints	
Research blood and plasma	sma	×					See	footnote	12 for deta	See footnote 12 for details and timepoints	oints	
*Indicate	es evalua CBC with	tions are cu r differential cated on the	*Indicates evaluations are currently performed as standard of care at the MCW BMT program. 1. CBC with differential will be performed as appropriate during hospitalization for alloHC davs indicated on the schedule of events.	d as st d as al ents.	andard of	f care at	the MCW hospitaliz	/ BMT pro ation for a	gram. alloHCT on	clinic visits a	es evaluations are currently performed as standard of care at the MCW BMT program. CBC with differential will be performed as appropriate during hospitalization for alloHCT on clinic visits and at minimum performed on days indicated on the schedule of events.	verformed on

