MCW Protocol No: PRO00035737 24 Version No. 7 ADA testing is testing for anti-drug antibodies, while Nab testing is testing for neutralizing antibodies to give a more complete picture along with the PK testing. ADA testing typically includes 3 tiers- screen, confirm and titer where screen/confirm are qualitative (positive or negative) and titer is semi-quantitative. The Nab method for tildrakizumab is screen tier only and qualitative (positive or negative), in which only samples that test positive are confirmed in the ADA assay. The purpose of having ADA/Nab testing alongside the PK testing is to better understand the PK profile differences seen. For instance, if PK serum concentrations are lower for an individual then a high ADA response would provide more clarity regarding the serum levels. Nab testing then would give additional insight into the mode of action of the immunogenicity.

10. Incidence of infections

The incidence of grade ≥3 (CTCAE v5) viral, fungal, and bacterial infections will be determined. The cumulative incidence of CMV viremia post-alloHCT will be described.

11. Donor cell chimerism

Chimerism will be evaluated using sorted whole blood in CD3+ and CD33+ fractions. Mixed chimerism is defined as the presence of donor cells, as a proportion of total cells to be >5% and <95%. Full donor chimerism is defined as $\ge95\%$ of donor cells. Donor cells of $\le5\%$ will be considered as graft rejection. Donor cell chimerism will be assessed for all patients at day +28 (baseline) for both CD3+ and CD33+ fractions. The proportion of patients with each level of chimerism listed above will be described. CD3+ donor cell chimerism will be used to define the donor/recipient chimerism status.

12. Microbiome

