3.2 Treatment Schema

Patients enrolled on this clinical trial will receive tacrolimus initiating at day -3 at doses to maintain therapeutic levels per institutional preference and continued until at least day +90 post-transplant. Methotrexate will be administered intravenously and dosed at 15 mg/m² days +1, and 10 mg/mg² on days +3, +6 and +11. Tildrakizumab will be administered subcutaneously at a dose of 100 mg on day -1, day 28±3, day 112±7, day 196±14, and day 280±14.

Number of patients who will be enrolled in the study: 55.

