6.6 Follow-up Period

Patients will be followed for a total 12 months or until death, whichever occurs first. All patients who receive at least one dose of the study drug will be followed.

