7.2 Collection and Reporting Requirements for Adverse Events and Serious Adverse **Events**

Only grade 3,4 and 5 adverse events (including SAEs) must be recorded in OnCore[®] and/or an adverse event log. All AEs required to be collected must be graded according to the CTCAE v5. When possible, signs and symptoms indicating a common underlying pathology should be noted as one comprehensive event. Investigator's or treating physician's assessment of AE attributions must also be documented.

AEs will be collected from the time the subject signs the consent form through 30 days post last dose of study drug(s). AEs will be tracked and followed until resolution, subject withdraws consent, or is lost to follow-up (including subjects who discontinue early). All adverse events collected per the protocol will be followed with appropriate medical management until they are resolved, if they are related to the study treatment, or until the investigator deems the event to be chronic. Please see section 7.2.2 and Table 1 to identify the adverse events that need to be reported.

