10.3.2 Secondary Analysis (or Analysis of Secondary Endpoints)

The secondary endpoints will be evaluated in the efficacy analysis set. Time-to-event outcomes with and without competing risks will be analyzed using Kaplan-Meier and Nelson-Aalen estimates, respectively, and presented with 95% confidence intervals. Binary outcomes will be analyzed using proportions and presented with 95% confidence intervals.

Bacterial community composition will be characterized using OTU counts generated as described above. OTU counts will be converted to measures of relative abundance to account for variation in sequencing coverage between samples. Statistical analysis will be carried out using the statistical software package R (www.r-project.org). Alpha (α) diversity (richness and evenness of taxa within a population) will be reported using the Shannon Index⁴⁶ and Chao1 richness estimator. ⁴⁷ Beta (β) diversity (overlap in taxa shared between populations) will be analyzed using the Bray-Curtis dissimilarity metric⁴⁸ in conjunction with multivariate statistical analysis methods that will include Principal Components Analysis (PCA) and Permutational Multivariate Analysis of Variance (PERMANOVA).⁴⁹ Changes in abundance of individual taxa will also be analyzed using traditional univariate statistical methods.

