APPENDIX 3. MEDICATION GUIDE

ILUMYA™ - tildrakizumab-asmn injection, solution Sun Pharmaceutical Industries, Inc.

Medication Guide

ILUMYA™ ("e-loom'-me-a") (tildrakizumab-asmn)

injection, for subcutaneous use

What is the most important information I should know about ILUMYA™?

ILUMYA™ may cause serious side effects, including:

Serious allergic reactions. Get emergency medical help right away if you get any of the following symptoms of a serious allergic reaction:

- feel faint
- swelling of your face, eyelids, lips, mouth, tongue or throat
- skin rash
- trouble breathing or throat tightness
- chest tightness

Infections. ILUMYA™ is a medicine that may lower the ability of your immune system to fight infections and may increase your risk of infections. Your healthcare provider should check you for infections and tuberculosis (TB) before starting treatment with ILUMYA™ and may treat you for TB before you begin treatment with ILUMYA™ if you have a history of TB or have active TB. Your healthcare provider should watch you closely for signs and symptoms of TB during and after treatment with ILUMYA™.

Tell your healthcare provider right away if you have an infection or have symptoms of an infection, including:

- fever, sweats, or chills
- cough
- shortness of breath
- blood in your phlegm (mucus)
- muscle aches
- warm, red or painful skin or sores on your body different from your psoriasis
- weight loss
- diarrhea or stomach pain
- burning when you urinate or urinating more often than normal

See "What are the possible side effects of ILUMYA™?" for more information about side effects.

What is ILUMYA™?

ILUMYA™ is a prescription medicine used to treat adults with moderate to severe plague psoriasis who may benefit from taking injections, pills (systemic therapy) or treatment using ultraviolet or UV light (phototherapy).

MCW Protocol No: PRO00035737 61 Version No. 7 Version Date: 10/31/2022 It is not known if ILUMYA™ is safe and effective in children under 18 years of age.

Do not use ILUMYA™ if you have had a severe allergic reaction to tildrakizumab or any of the other ingredients in ILUMYA™ . See the end of this Medication Guide for a complete list of ingredients in ILUMYA™.

Before receiving ILUMYA™, tell your healthcare provider about all of your medical conditions, including if you:

- have any of the conditions or symptoms listed in the section "What is the most important information I should know about ILUMYA™?"

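### The plan does not say which CMV tests feed the cumulative incidence of viremia; the four scheduled tests alone would probably under-count it over 12 months

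*Combined protocol and SAP*

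**What the plan says.** Section 2.5, item 10 (incidence of infections) covers grade 3 or higher viral, fungal and bacterial infections and then adds: "The cumulative incidence of CMV viremia post-alloHCT will be described". Nothing further is said about this measure. Other items in Section 2.5 are fuller: acute GVHD has days 100 and 180 with death as the competing event, and NRM has day 100 and one year with relapse or progression as the competing event.

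In the Study Calendar, the row "CMV NAAT peripheral blood" is marked in the day 28, 56, 100 and 112 columns only. The row carries an asterisk, explained as "evaluations are currently performed as standard of care at the MCW BMT program". The CBC and metabolic panel footnotes make the listed days a minimum on top of clinic visits, and the GVHD footnote also calls its days a minimum. The CMV row has no such footnote.

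On dosing, Section 3.2 says: "Tildrakizumab will be administered subcutaneously at a dose of 100 mg on day -1, day 28±3, day 112±7, day 196±14, and day 280±14". On follow-up, Section 6.6 says: "Patients will be followed for a total 12 months or until death, whichever occurs first". Section 13.5 has study data entered on CRFs in line with the study calendar. On adverse events, Section 7.2 says: "Only grade 3,4 and 5 adverse events (including SAEs) must be recorded in OnCore", with collection ending 30 days after the last dose.

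On estimation, Section 10.3.2 says: "Time-to-event outcomes with and without competing risks will be analyzed using Kaplan-Meier and Nelson-Aalen estimates, respectively". Infections do not appear in the secondary endpoint list in Section 10.1.

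**The concern.** A cumulative incidence counts first events from a time origin to a horizon. That requires a rule for which observations can establish an event and when the event is taken to have happened. Here the origin is transplant, the horizon is not stated, and the only CMV observations that the plan names are four tests in the first 112 days. Read literally, an episode that begins and clears between two tests is never an event, and neither is lower-grade viremia that begins after day 112. The third dose falls at the visit of the last scheduled test and two more doses follow, so no scheduled CMV test can describe the period under doses 3 to 5.

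This matters because the trial adds an antibody to tacrolimus and methotrexate, and the medication guide in Appendix 3 warns that the drug "may increase your risk of infections". A low reported rate could reflect the test dates rather than the patients. Two analysts, one using the four calendar results and one using the full chart, could report materially different rates, and both would be within the plan.

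**Working it through.** The plan states no expected CMV rate, so there is no figure of its own to reproduce.

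**Inputs from the documents.** Tests at days 28, 56, 100 and 112 (Study Calendar). Doses at days -1, 28, 112, 196 and 280 (Section 3.2). Follow-up of 12 months (Section 6.6). Nominal days are used throughout.

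**Calendar arithmetic.** Gaps between observations, from day 0: 28, 28, 44 and 12 days. The longest gap, 44 days (100 − 56), is the longest delay in dating an onset. Scheduled testing spans 112/365 = 31% of follow-up time. Doses on or after the last test: 3 of 5.

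**Short episodes.** Assumptions: one episode per patient, lasting L days, with onset s uniform over days 0-112, detected only if some test day t satisfies s ≤ t ≤ s + L. The detectable onsets are then the union of the intervals from t − L to t, within days 0-112.

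| L (days) | Detectable onset days | Caught | Missed |
|---|---|---|---|
| 14 | 14 + 14 + 26 = 54 | 54/112 = 48% | 52% |
| 21 | 21 + 21 + 33 = 75 | 75/112 = 67% | 33% |
| 28 | 28 + 28 + 40 = 96 | 96/112 = 86% | 14% |
| 44 or more | 112 | 100% | 0% |

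The last term in each of the first three rows merges the overlapping intervals for days 100 and 112 (for L = 14, days 86 to 112).

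**First four weeks alone.** For onset on days 0-28, the day-28 test catches 14/28 = 50%, 21/28 = 75% and 28/28 = 100% of episodes lasting 14, 21 and 28 days.

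**Shorter horizon.** For onset uniform over days 0-100, the tests catch 3 × 14 = 42, 3 × 21 = 63 and 3 × 28 = 84 of 100 onset days. The missed shares are 58%, 37% and 16%.

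**Twelve-month horizon.** If a share q of first episodes starts after day 112, overall capture is (1 − q) × the share caught above. The documents give no q, so a range is assumed.

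| q | L = 14 | L = 21 | L = 28 | L = 44 or more |
|---|---|---|---|---|
| 10% | 43% | 60% | 77% | 90% |
| 30% | 34% | 47% | 60% | 70% |

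**Opposing effect of the estimator.** As worded, Section 10.3.2 assigns Kaplan-Meier to outcomes with competing risks. Censoring deaths inflates the estimate. Under constant hazards, with true cumulative incidence c and competing deaths d, the total hazard is H = −ln(1 − c − d) and Kaplan-Meier reads 1 − exp(−H × c/(c + d)). For an assumed c = 30%:
- d = 5%: H = 0.431, reading 30.9%.
- d = 10%: H = 0.511, reading 31.8%.

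The inflation is 0.9 to 1.8 percentage points. By comparison, 77% capture of a true 30% would leave 0.77 × 30% = 23.1%, a loss of 6.9 points. Under-capture is therefore the larger effect, unless episodes are long and nearly all begin by day 112.

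**The case against.** The strongest reply is that Section 2.5 does not confine the measure to the four calendar tests. The asterisk marks CMV testing as routine at the site, so the chart may hold many more results. The missing minimum-days footnote is weak evidence of restriction: history and physical examination also carries an asterisk without such a footnote, and nobody would conclude that no other examinations take place. This stands. A reader might infer that the cumulative incidence cannot be derived at all; the documents do not support that. What they leave open is how often routine testing is done and whether its results reach the dataset. Section 13.5 points towards calendar-only entry without settling it.

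A reader might also infer that the estimate is certain to be biased low. That is not supported either. No horizon is stated, and with a day-100 or day-112 horizon the end of testing costs nothing, although the gaps between tests still do. Episodes of 44 days or more that start by day 112 are all caught. Many episodes that start in the first four weeks are still present at day 28. The Kaplan-Meier wording pushes the estimate upward.

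Nor is it right that nothing about CMV would be known under doses 3 to 5. Grade 3 or higher viral infection belongs to the same item. Grade 3-5 events and all SAEs are collected to 30 days after the last dose, about day 310 (280 + 30) for a patient who receives all five doses. The gap is lower-grade viremia. Calendar footnote 8 does ask for a review of all toxicities at visits to 12 months, but Section 7.2 limits what must be recorded to grades 3-5. For a patient whose last dose is at day 28, adverse-event collection ends at about day 58.

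Finally, the measure is descriptive. No test, comparator or stopping rule depends on it, which limits the weight of the point but not the case for a cheap clarification.

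**Conclusion.** The point holds in conditional form. The plan leaves the data source, horizon, threshold and competing event for CMV viremia undefined. If the four scheduled results are the only source, the measure would probably be too low over 12 months. Missed shares are 52%, 33% and 14% for episodes of 14, 21 and 28 days with onset on days 0-112, and zero from 44 days. If 10% to 30% of first episodes start after day 112, overall capture is 43% to 34%, 60% to 47% and 77% to 60% for those three lengths. Onset dates may be up to 44 days late.

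These sizes rest on assumed episode lengths, uniform onset, one episode per patient and an assumed late share, none of which the documents supply. If all routine results are used and testing is frequent, the loss could be small. The primary analysis is unaffected. The change is worth making because the measure belongs to a safety-related secondary endpoint and the remedy is inexpensive.

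**What to change.** In Section 2.5, item 10, and in the calendar footnotes and CRF:

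- Count every CMV NAAT result obtained as standard of care from day 0 to a stated horizon (12 months, or day 100 or 112 if that is what is intended). Record the date and value of each.
- State the positivity threshold, and take the date of the first result meeting it as onset.
- Estimate the cumulative incidence function with death without viremia as the competing event, and make Section 10.3.2 say so for this measure in place of Kaplan-Meier.
- Add infections, including CMV viremia, to the Section 10.1 list so that the two sections agree.

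If only the scheduled results will be used, report the measure as CMV viremia detected at the day 28, 56, 100 or 112 test, and do not call it a post-transplant cumulative incidence.

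The cost is protocol wording, a CRF field and abstraction of results already in the chart. No tests are added and patient management is unchanged. The reported rate will probably be higher than under the four-test reading.

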(overlap in taxa shared between populations) will be analyzed using the Bray-Curtis dissimilarity metric⁴⁸ in conjunction with multivariate statistical analysis methods that will include Principal Components Analysis (PCA) and Permutational Multivariate Analysis of Variance (PERMANOVA).⁴⁹ Changes in abundance of individual taxa will also be analyzed using traditional univariate statistical methods.

2.6 Correlative Studies

We intend to perform correlative studies to understand the impact of anti-IL-23 antibody treatment post allogeneic hematopoietic progenitor cell transplantation. This testing should help us better understand the changes that are happening within the immune system to inhibit graft-versus-host disease (GVHD). We propose obtaining labs at a minimum of nine time points as follows:

- Baseline blood and plasma samples (at screening).
- II) Blood and plasma samples at the following time points: days 7±3, 14±3, 21±3, 28±7, 60±14, 90±14, 196±30, 365±30 post-transplant.
- III) Samples at the time of development of GVHD (if it occurs).

3 STUDY DESIGN

3.1 General Description

This is a phase II, open-label, single-arm trial designed to evaluate the efficacy of tildrakizumab in improving GVHD relapse-free survival.

Prior to embarking on the phase II portion of the study, we proposed a run-in of six patients to assess the safety and tolerability of tildrakizumab in patients undergoing MAC alloHCT. These six patients received the same dosing schema as the other patients in our proposed phase II study. The first three patients were followed through day 28 to ensure no evidence of primary graft failure. We saw no evidence of primary graft failure, thus, an additional three patients (similar to a 3+3 trial design) were treated on study and again, monitored through day 28 for evidence of primary graft failure. No evidence of graft failure was seen in these six patients. Thus, additional patients will be enrolled in the trial until the trial has reached full accrual or activated a stopping rule.

3.2 Treatment Schema

Patients enrolled on this clinical trial will receive tacrolimus initiating at day -3 at doses to maintain therapeutic levels per institutional preference and continued until at least day +90 post-transplant. Methotrexate will be administered intravenously and dosed at 15 mg/m² days +1, and 10 mg/mg² on days +3, +6 and +11. Tildrakizumab will be administered subcutaneously at a dose of 100 mg on day -1, day 28±3, day 112±7, day 196±14, and day 280±14.

Number of patients who will be enrolled in the study: 55.

3.3 Rationale for Treatment Schema

We propose early administration of tildrakizumab for acute GVHD prevention based on the fact

that immediately following MAC, tissue injury ensues resulting in release of inflammatory mediators that provoke acute GVHD. We hypothesize that it is critical to have tildrakizumab present in order to block this inflammatory milieu, as outlined in Section 1.3. We propose continued administration of tildrakizumab to mediate a beneficial effect not only on the risk of aGVHD but also on cGVHD. The FDA-approved dosing of tildrakizumab for moderate to severe plaque psoriasis, based on a half-life of 21 to 24 days, is week 0, week 4 and every 12 weeks thereafter. We have maintained this dosing schedule [day -1 = week 0, day 28=week 4, day 112, day 196, day 280 are on the every-12-week schedule] and continued the tildrakizumab dosing through the period at highest risk for development of acute GVHD, conventionally thought to occur prior to day 100, and into the period of time during which chronic GVHD can occur, traditionally after day 100.

3.4 Study Completion

The study will reach study completion 24 months from the time the study opens to accrual.

4 SUBJECT PARTICIPATION, DISCONTINUATION, AND WITHDRAWAL

MCW must follow all MCW IRB requirements and policies regarding subject participation, found here:

https://www.mcw.edu/HRPP/Policies-Procedures.htm

4.1 Subject Status

Subject statuses throughout the trial are defined as follows:

- Prescreening: preconsent (subject considering trial or study staff considering patient for the trial per institutional recruitment methods).
- Screening: period after consent, but prior to eligibility confirmation.
- Consented: consented, prior to eligibility confirmation.
- Eligible: the local investigator confirms all eligibly criteria apply.
- On study/enrolled: date eligibility is confirmed.
- On arm: date of enrollment.
- On treatment: first day treatment was given to the last day treatment was given.
- Off treatment: the last day treatment was given.
- On follow-up: from last day of treatment to the end of follow-up period.
- Off study: follow-up period completed, with no additional data gathered.
- Withdrawn: subject fully withdraws consent (i.e., refuses ALL follow-up, even survival) or is taken off study by the local PI.

